**Table 3**

Intercurrent Event Estimation Rules (to be applied sequentially)	Intercurrent Event (IE)	Strategy with Rationale	Estimation Method following IE
1	
None (completed as randomised)
 
Without discontinuation of CIS feedback or ELLIPTA maintenance sensor
 
 
Premature discontinuation from rescue/salbutamol MDI sensor
 
Change of dose of ELLIPTA
 
 
Discontinuation of CIS feedback, but not ELLIPTA maintenance sensor
 
 
Premature discontinuation from App and/or HCP interaction
 
	
Treatment policy:
 
Directly assessed using observed adherence data while ELLIPTA maintenance sensor is in use, regardless of whether the CIS feedback is discontinued.
	Data are available; no imputation required
2	Discontinuation of ELLIPTA maintenance sensor only	
Treatment policy:
 
Without the ELLIPTA maintenance sensor, no CIS feedback is possible, assume
 
 
participants continue to take ELLIPTA as
 
	Jump to Reference (J2R) Imputation

Intercurrent Event Estimation Rules (to be applied sequentially)	Intercurrent Event (IE)	Strategy with Rationale	Estimation Method following IE
		
they would have without the CIS intervention
 
 
adherence will be like that in the control (no CIS feedback) group
 
	
3	Discontinuation of ELLIPTA	Whilst on treatment:	Follow-up after ELLIPTA discontinuation is excluded, i.e. no data; adherence is weighted by proportion of months 4 to 6 for which data is included*
4	Premature withdrawal from the study, not related to ELLIPTA discontinuation or CIS, and concurrent with discontinuation of the ELLIPTA maintenance sensor	Hypothetical:	Missing at Random (MAR) Imputation

* Discontinuation of ELLIPTA prior to the start of month 4 will lead to a participant being excluded from the primary analysis
			

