#### **7.1.4.2. Events following premature discontinuation of the ELLIPTA maintenance sensor**

It is assumed that participants would continue to take ELLIPTA as they would have without the CIS intervention (J2R imputation) following discontinuation of the ELLIPTA maintenance sensor.

It is assumed that ELLIPTA treatment is no longer appropriate if the participant discontinues ELLIPTA but remains in the study or withdraws for a reason related to ELLIPTA. The ELLIPTA adherence endpoint is no longer considered relevant and subsequent follow-up is excluded from the analysis, with participants weighted in the analysis by the proportion of months 4 to 6 for which data is included.

It is assumed that participants would continue to take ELLIPTA as they would have with their allocated CIS intervention (MAR imputation) following concurrent discontinuation of the ELLIPTA maintenance sensor and withdrawal unrelated to ELLIPTA or CIS.

See Section 10.5.3.1 ELLIPTA Device Sensor Assessments for further derivation details.

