### 7.1.5.1. Statistical Methodology Specification

Endpoint / Variables
The primary endpoint is the percentage of ELLIPTA doses taken (daily adherence) between the beginning of Month 4 and the end of Month 6 as determined by the maintenance sensor. Daily adherence is defined as the participant taking one dose of Relvar/Breo ELLIPTA within a 24 hour period, starting at 12.00am each day of treatment period.
Multiple Imputation Specification
Imputation will be carried out using monthly adherence rates for months 1 to 6. 1000 draws will be used. For each draw, four intermediate imputation datasets will be created to allow for the handling of fully unobserved months (using set A imputations) and partially unobserved months (using set B imputations).

 
• Set A where the partially observed month is directly estimated under the MAR assumption as the proportion of the number of days a participant is adherent divided by the number of days data provided in that month. 
 
• J2R imputations
 
• MAR imputations
 
 
 
• Set B where the partially observed month is set to missing. 
 
• J2R imputations
 
• MAR imputations
 
 
 

The timing of the intercurrent events of discontinuation of the ELLIPTA maintenance sensor, discontinuation of ELLIPTA and withdrawal from study will be used to identify the proportion of each month to be assigned as observed data, J2R imputed data, MAR imputed data, or no data. The strategy for handling intercurrent events is described in Section 7.1.4 Strategy for Intercurrent (Post-Randomisation) Events.
 
Within each imputation draw, for each month, the observed and any imputed data will be combined to provide a percentage adherence value. The values for months 4 to 6 will be combined to create the value for the primary analysis and the weight to be assigned to each participant.
 
Multiple imputation using Rubin's rules will be used to estimate the treatment effect and associated standard error, by performing the ANCOVA analysis described below on the primary endpoint within each dataset.
 
The multiple imputation will be implemented using the methods described in Carpenter, 2013, using the macros available from https://missingdata.lshtm.ac.uk/2017/04/06/gsk-five-macros/.

Model Specification

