
2. Duplicate the observed monthly adherence values dataset (Observed Dataset A). Using the values in the duplicate dataset (Dataset B), impute the month where the sensor was permanently discontinued before the end of that month (and therefore presents a monthly adherence rate based on partly observed sensor data for that month) as missing unless the participant is a study completer.
 
3. Using each of the two observed datasets (Observed Dataset A and Observed Dataset B), create four separate imputed datasets (J2R-Dataset A, J2R-Dataset B, MAR-Dataset A, MAR-Dataset B) that account for the two imputation methods (J2R or MAR) that may be applied to participants' data after discontinuation of the maintenance sensor, ELLIPTA or withdrawal from study. Imputation will be carried out using observed monthly adherence rates for months 1 to 6. 1000 draws will be used. Completely missing intermediate monthly values will be assumed MAR. The multiple imputation will be implemented using the methods described in Carpenter, 2013, using the macros (Part1A, Part1B, Part2A and Part2B) available from https://missingdata.lshtm.ac.uk/2017/04/06/gsk-five-macros/ using seeds documented in the RAP for the respective endpoint.
 
4. The Observed Datasets (A and B), imputed datasets (J2R-Dataset A, J2R-Dataset B, MAR-Dataset A, MAR-Dataset B) and the timing of the intercurrent events; permanent discontinuation of the ELLIPTA maintenance sensor; permanent discontinuation of ELLIPTA treatment and withdrawal from study; will be used to create an analysis dataset (Dataset C) that identifies the proportion of each month to be assigned as observed data, J2R imputed data, MAR imputed data, or no data. The strategy for handling intercurrent events is described in Section 7.1.4 Strategy for Intercurrent (Post-Randomisation) Events.
 
Within each imputation draw, for each missing month, the observed and any imputed data will be combined to provide a percentage adherence value. The values for months 4 to 6, months 1-3 and months 1-6, will be combined to create the value for the respective primary and secondary endpoint analyses and the weight to be assigned to each participant.
 
5. Analyse using Multiple Imputation macro Part3
 

Perform ANCOVA on the endpoint for each imputed dataset to obtain treatment effect estimate and standard error

Combine estimates across imputations using Rubin's rules

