
Percentage of ELLIPTA doses taken (daily adherence) Endpoint
$\text{Monthly observed maintenance adherence (\%)} = \left( \frac{D1}{D5 - D2 - D3} \right) \times 100$

STEP 2: Creating the modified observed adherence dataset (Observed Dataset B)
 
The Observed Dataset A will be duplicated. Using the values in the duplicate dataset (Observed Dataset B) the Analysis Month where the maintenance sensor was permanently discontinued before the end of that month (and therefore presents a monthly adherence rate based on partly observed sensor data for that month) will be imputed as missing; i.e. in Dataset B, if within an Analysis Month (<math>D3 > 0</math> and <math>D3 < D5</math>) then set monthly value for that Analysis Month to missing. (Note: unless the participant is a completer in which case do not set the value to missing for that Analysis Month)

STEP 3: Creating the reference imputed datasets under MAR and J2R method
 
Using each of the two observed datasets (Observed Dataset A and Observed Dataset B) monthly values, create four separate reference imputed datasets (J2R-Dataset A, J2R-Dataset B, MAR-Dataset A, MAR-Dataset B) that account for the two imputation methods (J2R or MAR). Completely missing intermediate monthly values will be assumed MAR.
 
The multiple imputation will be implemented using the methods described in Carpenter, 2013 using macros, Part1A, Part1B, Part2A and Part2B (available from https://missingdata.lshtm.ac.uk/2017/04/06/gsk-five-macros/). The seeds are documented at the end of Section 10.5.3.1. and 1000 draws will be used in the relevant macros parameters.
 
Due to the range of the monthly adherence percentages being limited between 0 and 100, the multiple imputation process can generate percentages outside the possible range of values (< 0% or > 100%). A cap will be put in place where values imputed < 0 will be set as 0 and values imputed as > 100 set as 100.

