
STEP 4: Creating the Monthly Analysis values dataset
 
For each month within each participant create a count of each of the following durations based on intercurrent events: Let,
 
<math>m1</math> = maintenance sensor still in use
 
<math>m2</math> = maintenance sensor discontinued, but ELLIPTA Relvar/Breo not discontinued
 
<math>m3</math> = ELLIPTA Relvar/Breo discontinued (includes days post withdrawal from the study). Note, if participant is a completer then for Analysis Month 6, <math>m3=0</math>.
 
<math>m4 = m1 + m2 + m3</math>
 
Calculate the proportion of days the sensor was still in use from the total number of days ELLIPTA was in use within a month, <math>m1/(m1+m2)</math>
 
Calculate the proportion of days the sensor was discontinued from the total number of days ELLIPTA was in use within a month, <math>m2/(m1+m2)</math>
 
Set participants monthly values to observed, MARA, MARB, J2RA, J2RB imputation, no data each with an <math>m1</math>, <math>m2</math>, <math>m3</math> and <math>m4</math> duration.

Percentage of ELLIPTA doses taken (daily adherence) Endpoint												
--	--	--	--	--	--	--	--	--	--	--	--	--

Examples include to following:

- A participant who prematurely discontinues sensor after 15 days of Analysis Month 5 and concurrently discontinues ELLIPTA maintenance therapy and study withdrawal after 10 days of Analysis Month 6

Subject Id	Draw	Month	A	B	J2RA	J2RB	MARA	MARB	m1	m2	m3	m4
X	1	1	77	77	77	77	77	77	28	0	0	28
X	1	2	82	82	82	82	82	82	28	0	0	28
X	1	3	87	87	87	87	87	87	28	0	0	28
X	1	4	77	77	77	77	77	77	28	0	0	28
X	1	5	71	.	71	77	71	78	15	13	0	28
X	1	6	.	.	80	79	77	76	0	10	18	28

- A participant who concurrently prematurely discontinues sensor, ELLIPTA maintenance therapy and study withdrawal after 15 days of Analysis Month 5

Subject Id	Draw	Month	A	B	J2RA	J2RB	MARA	MARB	m1	m2	m3	m4
X	1	1	77	77	77	77	77	77	28	0	0	28
X	1	2	80	80	80	80	80	80	28	0	0	28
X	1	3	79	79	79	79	79	79	28	0	0	28
X	1	4	75	75	75	75	75	75	28	0	0	28
X	1	5	83	.	83	77	83	79	15	0	13	28
X	1	6	.	.	77	77	75	80	0	0	28	28

- A participant who completes the study after 26 days in Analysis Month 6

Subject Id	Draw	Month	A	B	J2RA	J2RB	MARA	MARB	m1	m2	m3	m4
X	1	1	77	77	77	77	77	77	28	0	0	28
X	1	2	82	82	82	82	82	82	28	0	0	28
X	1	3	87	87	87	87	87	87	28	0	0	28
X	1	4	77	77	77	77	77	77	28	0	0	28
X	1	5	80	80	80	80	80	80	28	0	0	28
X	1	6	82	82	82	82	82	82	15	11	0	26

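### A study completer who stops only the ELLIPTA sensor keeps pre-stop adherence for the rest of the stop month, although the SAP assigns jump-to-reference to that time

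*SAP*

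**What the plan says.** **The declared handling.** SAP Section 7.1.4, Table 3, rule 2 names the event "Discontinuation of ELLIPTA maintenance sensor only" and gives its method as "Jump to Reference (J2R) Imputation". Section 7.1.4.2 states the assumption: "It is assumed that participants would continue to take ELLIPTA as they would have without the CIS intervention (J2R imputation) following discontinuation" of the sensor. The schematic in Section 10.5.3.1 draws this as pattern B, with J2R running from the sensor stop to the end of the six months. SAP Section 2.1, Table 1 lists the move from study withdrawal to sensor discontinuation as a deliberate change from the protocol, because the sensor can be given up by someone who stays in the study.

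**The stop month.** Monthly adherence is held in two copies. Dataset A keeps the rate over the observed days. Dataset B is meant to blank the month in which the sensor stopped, so that a value can be imputed for the unobserved days. On Dataset B the SAP says two things:

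- Section 7.1.5.1: "Set B where the partially observed month is set to missing", with no exception.
- Section 10.5.3.1: the overview (item 2) sets the month "as missing unless the participant is a study completer", and Step 2 repeats the exception: "unless the participant is a completer in which case do not set the value to missing for that Analysis Month". Neither limits it to Month 6 or mentions an early Visit 10.

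**Who is a completer.** SAP Section 10.6.1 defines study completion by visits and the follow-up contact, with no condition on the sensor. Protocol Sections 5.1 (Early Withdrawal Visit) and 8 encourage people who stop the CIS to stay in the study.

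**The concern.** The participant described by pattern B, who drops the sensor but stays on ELLIPTA and in the study, is ordinarily a study completer. Step 2 therefore exempts that participant from the one operation that would bring control-arm information into the stop month. Dataset B equals Dataset A, the J2R version of Dataset B (J2RB) equals the observed value, and the Step 4 average has nothing imputed to draw on. Later whole months are missing in Dataset A and do take a J2R value, so one participant is handled under two assumptions.

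Two things are at stake. The primary endpoint departs from its declared estimand for these participants in that month. And two programmers, one following Section 7.1.5.1 and one following Section 10.5.3.1, would build different datasets.

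**Working it through.** **Inputs.** From SAP Section 10.5.3.1, Step 4: m1 = days with the sensor in use, m2 = days after the sensor stop while still on ELLIPTA, and the printed examples. From Protocol Section 11.2.1: a 15-point difference, SD 28, 76 per arm. From Protocol Section 11.2.2: adherence of 88% and 66% in the cited adult reminder study, used only as a second, larger gap. The documents give neither the share of participants who stop the sensor nor their adherence relative to control, so both are assumed below.

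**Formula (Step 4, sensor in use for at least one day of the month).** Analysis value = m1/(m1+m2) × J2RA + m2/(m1+m2) × J2RB.

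**1. The SAP's completer example** ("A participant who completes the study after 26 days in Analysis Month 6"). Month 6 has m1 = 15, m2 = 11, m3 = 0, m4 = 26, and every value column is 82:
15/26 × 82 + 11/26 × 82 = 82.0.
The 11 days after the sensor stop carry the observed value.

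**2. The SAP's first example, a non-completer.** Month 5 has m1 = 15, m2 = 13, observed 71, Dataset B missing, J2RB = 77:
15/28 × 71 + 13/28 × 77 = 73.8.
The same month in a completer would have J2RB = 71 and give 71.0. Here the exemption lowers the month by 2.8 points, which is 2.8/3 = 0.9 on a three-month mean.

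**3. The completer example without the exemption.** The SAP gives no control-based draw for this participant, so a range is assumed. The printed Month 4-6 mean is (77 + 80 + 82)/3 = 79.7.

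| Assumed J2RB | Month 6 value | Fall in Month 4-6 value |
|---|---|---|
| 77 | 79.9 | 0.7 |
| 70 | 76.9 | 1.7 |
| 66 | 75.2 | 2.3 |
| 60 | 72.7 | 3.1 |

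**4. General size for one participant.** With a sensor stop after day d of a 28-day month in Months 4-6, and a gap g between own pre-stop and control-based adherence, the shift in the Month 4-6 value is g × (28 − d)/28 ÷ 3.

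- g = 15: d = 1, 7, 14, 21, 27 gives 4.8, 3.75, 2.5, 1.25, 0.2.
- g = 22 (88 − 66): d = 1, 14, 27 gives 7.1, 3.7, 0.3.

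**5. Size in the arm mean.** If a share p of the arm stops mid-month in Months 4-6, half a month in on average, and completes, the shift is p × g × 0.5/3.

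- g = 15: p = 5% gives 0.125; p = 10% gives 0.25.
- Wider range: p = 2%, g = 15 gives 0.05; p = 15%, g = 22 gives 0.55.

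The standard error of the difference under the plan is 28 × √(2/76) = 4.54, so 0.125 to 0.25 is about 3% to 6% of it.

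**6. Scope.** A stop before Month 4 leaves the primary endpoint untouched by this exemption, but affects the Month 1-3 and Month 1-6 endpoints. A participant who stops the sensor first and withdraws later is not exempt. Section 10.5.3.2 repeats the exemption for rescue-free days (overview item 2 and Step 2), with a matching completer example: r1 = 15, r2 = 12, all values 82.

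**The case against.** **A narrower meaning of completer.** The schematic in Section 10.5.3.1 labels only pattern A (sensor kept to the end) as the completer and lists sensor-only stops separately as pattern B. On that labelling Step 2 would not exempt pattern B. But the overview says study completer, Section 10.6.1 defines study completion without reference to the sensor, and the completer example has 11 days classed as sensor stopped, all within the 26 days up to completion. The labelling is a reason to define the term; it does not remove the conflict.

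**An early Visit 10 as the purpose.** A reader might infer that the exemption exists only for completers whose Visit 10 falls before Day 168. No passage says so, and Table 5 (Section 10.2.2) already ends Month 6 at Visit 10 for completers, so those later days are not counted.

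**Table 5 may switch Step 2 off.** This stands in part. Table 5 also ends a month at discontinuation. Read literally, the count of post-discontinuation days (D3) is zero in every stop month, Step 2 never triggers, and the exemption changes nothing. However, the first two examples show a full 28-day count with the Dataset B value missing, so the full count is evidently intended. The two passages have to be settled together.

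**Direction.** A reader might infer that the exemption always flatters the CIS arms. The documents do not support that. The sign depends on whether pre-stop adherence lies above or below the control-based draw, and in the SAP's first example it lies below (71 against 77). Nothing in the documents says how well people who give up the sensor were adhering beforehand.

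**Size.** The stopping share has no source. Protocol Section 8 offers people who leave the CIS the option to stay with the ELLIPTA sensor attached, and those people fall under rule 1, which needs no imputation. The group concerned may be small.

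**Conclusion.** The inconsistency is real. For a completer who stops only the sensor, Section 10.5.3.1 does not carry out the J2R handling that Table 3, Section 7.1.4.2 and pattern B declare, and it contradicts Section 7.1.5.1 on Set B. It is confined to one month per such participant.

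The shift is towards the CIS arms when pre-stop adherence exceeds the control-based draw, and the other way otherwise. At an assumed 15-point gap it reaches 4.8 points in one participant's Month 4-6 value, and about 0.1-0.25 points in the arm mean if an assumed 5-10% stop mid-month.

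A reader might go further and infer that rule 2 is not applied at all, or that the primary result is at risk. Neither follows: whole months after the stop are J2R, and a shift of this size is unlikely to change the conclusion. This is a minor correction, worth making so that the primary analysis matches its estimand and can be reproduced.

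**What to change.** - **Limit the exemption.** In Section 10.5.3.1 (overview item 2 and Step 2), apply it only to completers whose sensor was in use up to Visit 10, or Day 168 if earlier. For any completer with a permanent sensor discontinuation before then, set the stop month to missing in Dataset B, so that J2RB fills the post-stop days.
- **Count the stop month in full.** State that the total day count (D5) for the stop month runs to the end of the month, or to Visit 10 in Month 6 for completers, so that D3 > 0 can trigger Step 2 as the first two examples imply. Align Table 5 with this.
- **Carry it to rescue-free days.** Make the same change in Section 10.5.3.2 (overview item 2 and Step 2), with J2RB or its missing-at-random counterpart MARB as the rescue rules require.
- **Correct the completer examples** in Step 4 of both sections.

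The cost is a few lines of SAP text and minor reprogramming. The Arm 1 estimate may move slightly in either direction.

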## **11.2. Sample Size Determination**

### **11.2.1. Sample Size Assumptions**

The fixed sample size calculation is based on the primary endpoint, percentage of ELLIPTA doses taken (daily adherence) between Months 4 and 6 as determined by the maintenance sensor and has approximately 90% power to detect an absolute difference of 15% in the primary comparison. The treatment difference is based on the limited published data [[Charles](#), 2007, [van Boven](#), 2016]. This assumes a conservative standard deviation of 28% (based on a previous study [[Charles](#), 2007]) and significance declared at the two-sided 5% level.

Approximately 432 patients will be randomised in order to obtain at least 380 subjects (i.e. 76 subjects per arm) with available data over the last three months of the treatment period, in anticipation of a 12% drop-out within the first three months. Subjects will be randomised to one of five treatment arms with a ratio of 1:1:1:1:1.

Using the above assumptions the smallest observed effect predicted to result in a statistically significant difference between treatment groups is 9% (minimum detectable difference).

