**Table 1 Changes to Protocol Defined Analysis Plan**

Protocol	Reporting & Analysis Plan	
Statistical Analysis Plan	Statistical Analysis Plan	Rationale for Changes
Duration of run-in included in analysis models as a continuous covariate, measured in days.	Duration of run-in included in analysis models as a categorical covariate of number of visits.	Participants can complete the run-in period in 1, 2 or 3 visits, use of a categorical covariate is more flexible than the assumption of a linear relationship.
Missing data due to a medical device incident will be assumed to be missing at random within the last 3 months treatment period.	Missing data due to a medical device incident will be assumed to be missing at random within each month of the treatment period.	Monthly adherence rates are used within the imputation model to allow for variation in adherence over time.
Participants who prematurely discontinue from study will have their post-withdrawal daily adherence data imputed using data from the control arm	Participants who prematurely discontinue from use of the ELLIPTA maintenance sensor will have subsequent adherence data imputed using data from the control arm	The ELLIPTA maintenance sensor may be discontinued without withdrawal from the study
Protocol Section 11.3 Populations for Analyses	RAP Section 4 Analysis Populations	The analysis populations have been updated to follow the study populations standard definitions and statistical displays

Protocol	Reporting & Analysis Plan	
Statistical Analysis Plan	Statistical Analysis Plan	Rationale for Changes
	Mean change from baseline (Randomisation) in ASUI and SGRQ total score at Month 6 included in the RAP as an additional endpoint	To support the exploratory summaries and analyses for ASUI and SGRQ continuous endpoint
Composite endpoint - Percentage of patients who have either an ACT total score of $\geq 20$ or an increase from baseline of $\geq 3$ in ACT total score at Month 6 (Visit 10).	Composite endpoint - Percentage of patients who have either an ACT total score of $\geq 20$ and/or an increase from baseline of $\geq 3$ in ACT total score at Month 6 (Visit 10).	The condition 'and/or' will be applied to the composite ACT endpoint to replace 'or' to clarify that participants who achieve both an ACT total score of $\geq 20$ and an increase from baseline of $\geq 3$ in ACT total score at Month 6, in addition to those who only achieve one, will be considered a responder.

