- If the sensor is in use for at least a day within a month, m1>0 then let the analysis value be a combined value (weighted average) of the J2RA observed and J2RB imputed values, by taking a proportion of each value based on the proportion of days sensor was still in use and discontinued whilst on ELLIPTA respectively;

Analysis value =  $m1/m1+m2 \times (\text{value from J2RA}) + m2/m1+m2 \times (\text{value from J2RB})$

Note the weight is,  $m1 + m2$

- Else if the sensor was not used in the month, m1=0 then let the analysis value be the imputed value,

Analysis value = value from J2RA dataset (which is the imputed value)

Implement special cases of J2R post-discontinuation of ELLIPTA by identifying participants where ELLIPTA is prematurely discontinued and the participant concurrently withdraws from the study, and ELLIPTA discontinuation reason is not related to ELLIPTA:

Percentage of ELLIPTA doses taken (daily adherence) Endpoint

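### As written, a trailing month lost entirely to device failure takes the jump-to-reference value, although the plan declares device-failure data missing at random (narrow case, small dilution)

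*SAP*

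**What the plan says.** **Declared assumption.** SAP Table 1 states: "Missing data due to a medical device incident will be assumed to be missing at random within each month of the treatment period". Protocol 11.4.1 makes the same MAR assumption for device, sensor and transmission failures. It computes adherence as adherent days over days with data across the last three months. SAP 7.1.4.1 repeats MAR, but in wording about intermittent data. In SAP Table 3, jump to reference (J2R) is tied to discontinuation of the maintenance sensor (rule 2), on the reasoning that adherence then resembles the control arm. Rule 1, where the sensor has not been discontinued, presumes that data exist and need no imputation.

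**Derivation (SAP 10.5.3.1).** Step 1 counts adherent days (D1), device-incident days (D2), days after sensor discontinuation (D3) and non-adherent days (D4), with total D5. The observed monthly rate is D1/(D5−D2−D3). On wholly missing months Step 3 says: "Completely missing intermediate monthly values will be assumed MAR". Step 4 then chooses the value for analysis. Its default is: "If the sensor is in use for at least a day within a month, m1>0 then let the analysis value be a combined value", the two parts being J2RA and J2RB, weighted by days with the sensor in use (m1) and days with it discontinued while ELLIPTA continues (m2). If m1=0 the value is J2RA. The MAR datasets enter Step 4 only when ELLIPTA discontinuation, sensor discontinuation and study withdrawal coincide.

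**The concern.** The protocol's three-month denominator gives an answer when Month 6 is wholly lost: adherence over Months 4 and 5. The SAP's move to monthly rates creates a month with no value at all, and that month has to be imputed. An interior month of this kind is covered by Step 3. No sentence covers a trailing one, and the default in Step 4 sends it to J2R.

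The participant's technical failure is then handled as though the sensor had been given up. J2R draws Arms 1 to 4 toward the Arm 5 mean. In Arm 5 the reference is the arm itself, so nothing changes on average. The primary contrast would be diluted by a rule that conflicts with the plan's own missing-data assumption.

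**Working it through.** **1. The plan's own figure.** Protocol 11.2.1 "has approximately 90% power to detect an absolute difference of 15% in the primary comparison". Inputs:

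| Input | Value | Source (protocol 11.2.1) |
|---|---|---|
| Difference | 15 points | as quoted above |
| SD | 28 points | "This assumes a conservative standard deviation of 28" |
| Test | two-sided 5% | "significance declared at the two-sided 5% level" |
| Evaluable per arm | 76 | "76 subjects per arm" |
| Allocation | equal, five arms | "with a ratio of 1:1:1:1:1" |

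SE = 28 × √(2/76) = 4.54. Power = Φ(15/4.54 − 1.96) = 91.0% (90.7% with the t distribution). Smallest significant difference = 1.96 × 4.54 = 8.9, against the stated 9. Randomised = 380/0.88 = 432. The stated figures reproduce.

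**2. Trace of Steps 1 to 4.** Take a 28-day Month 6 with D1=0, D2=28, D3=0, D4=0 and neither sensor nor ELLIPTA discontinued.

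- Step 1: the denominator is 28 − 28 − 0 = 0, so the value is missing in Dataset A.
- Step 2: Dataset B is a copy. Its rule for partly observed months needs D3>0 and does not apply, so the value is missing there too.
- Step 3: Month 6 is not intermediate, so each imputed dataset fills it by its own method.
- Step 4, failed sensor counted as in use (m1=28, m2=0): (28/28) × J2RA + (0/28) × J2RB = J2RA.
- Step 4, failed sensor counted as not in use (m1=0): J2RA.
- Route to MARA or MARB: needs the three concurrent discontinuations, which are absent here.

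The result is J2RA however m1 is counted. If Month 6 has even one day that is not a device incident, the denominator is positive, and removing the D2 days handles the loss as MAR.

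**3. Size per affected participant.** Assume the standard form of J2R, because the SAP leaves the details to its cited method and macros. With y the earlier months and B the regression of the missing month on them:

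- MAR mean: μ(own arm) + B(y − own-arm means)
- J2R mean: μ(Arm 5) + B(y − own-arm means)
- Difference: μ(own arm) − μ(Arm 5) = 15 at the design value, assumed constant over months

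The endpoint averages three months, so the loss is 15/3 = 5 points for one lost month and 2 × 15/3 = 10 for two. Simulation of six correlated months (within-person correlation 0.5, 0.7 and 0.9) gave 5.0 and 10.0. With the SAP's 0–100 cap and assumed means of 70 and 55, the losses were about 4.5 and 8.9.

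**4. Size on the treatment effect.** The documents do not give the share of Arm 1 affected; 2–10% is an assumed range. Uncapped:

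| Share affected | Month 6 lost: difference (power) | Months 5–6 lost: difference (power) |
|---|---|---|
| 0% | 15.00 (91.0%) | 15.0 (91.0%) |
| 2% | 14.90 (90.7%) | 14.8 (90.3%) |
| 5% | 14.75 (90.1%) | 14.5 (89.1%) |
| 10% | 14.50 (89.1%) | 14.0 (86.9%) |

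**5. Rescue free days (SAP 10.5.3.2).** The structure is the same. With r1=28 and r2=r3=0, the combined value reduces to J2RA in every feedback arm. For Arms 1 and 2 this sits oddly with SAP Table 4, which uses MAR there even after the MDI sensor is discontinued.

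**The case against.** **It is a gap, not a reversal.** Table 1 speaks of MAR within each month, which is done by dropping device-incident days; a month with no other days leaves that rule undefined. SAP 7.1.4.1 is limited to intermittent data. Step 4 labels its J2RA component as observed, so the authors evidently assumed data existed. This stands as an account of how the problem arose, and a reader who inferred that the SAP deliberately chose J2R for device failures would go beyond the text. It does not remove the problem. Table 1 and protocol 11.4.1 make no exception for a last month, and the written rules do return a value, from the J2R dataset.

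**J2R may be nearer the truth.** A sensor that yields no data for four weeks may also yield no feedback, which is the rationale of rule 2. That is fair. The dilution is therefore measured against the plan's declared assumption, not against a known truth.

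**The case is rare.** It needs a whole final month of incidents, no replacement sensor and no recorded permanent stop. Sensors are switched on at dispensing visits, inhalers hold 30 doses, and in Arms 1 and 3 the HCP reviews the data at least every four weeks. Sensor replacement is foreseen in the sensor-status table shell. All this lowers the likelihood without excluding the case: the same shell records malfunction separately from permanent stopping, so a failed but not discontinued sensor can be recorded.

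**A MAR analysis is already planned.** The generalised linear model sensitivity analysis uses no multiple imputation and assumes MAR. It may show the impact, but it does not correct the primary estimate.

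**Conclusion.** Wrong as written, and minor. For a trailing month made up wholly of device incidents, with the sensor not permanently discontinued, Step 4 returns J2RA where Table 1 and protocol 11.4.1 call for MAR.

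The loss is about 5 endpoint points per lost month for an affected participant in Arms 1 to 4, or about 4.5 after the cap at assumed means of 70 and 55. On the treatment effect that is 0.1 to 0.5 points for one month at an assumed 2–10% affected. The upper figure is 0.5/4.54 = 0.11 of the design standard error. These sizes rest on standard J2R, a constant 15-point difference and the assumed share.

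Two stronger readings should be resisted. A reader might infer that Arm 1 participants with a late sensor failure simply receive control-arm adherence. Only the wholly lost month is affected: with Month 6 lost, two thirds of the endpoint stays observed, and the imputed value still reflects the participant's own earlier months. A reader might also infer a material threat to the primary result. The documents give no failure rate to support that, and the direction is toward no effect.

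**What to change.** Add to Step 4 of SAP 10.5.3.1: *If every day of the month is a device incident (D2=D5, D3=0) and the sensor and ELLIPTA have not been discontinued, the analysis value is taken from MARA, whether the month is intermediate or last.* Days after permanent sensor discontinuation stay under rule 2 (J2R).

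The trigger should be D2=D5, not a zero denominator. D5−D2−D3=0 also holds for a month with 10 incident days followed by 18 days after discontinuation (28−10−18=0), and those 18 days belong to J2R under rule 2.

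Make the matching change for rescue free days in 10.5.3.2, with the condition referring to the MDI sensor and continued study participation.

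The cost is one sentence and one programming branch per endpoint. MARA is already generated, so no new imputation or seed is needed. The change should be made before unblinding.
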